We will use the continual reassessment method (CRM) design (O’Quigley et al., 1990) to find the optimal number of sessions to produce a clinically meaningful change in fMRI connectivity between the parietal cortex and hippocampus in healthy subjects. The CRM is an adaptive design for dose finding studies, in which a “dose-toxicity” curve is fitted to the data and each patient will be assigned the dose most likely to be associated with the target toxicity level, designated as maximum tolerated dose (MTD) (Garrett-Mayer, 2006). It is important to note that while we retain the toxicity terminology from the CRM literature in the following description, we have adapted the technique to finding the threshold for efficacy, not toxicity.

In our study, the escalation decisions will be based on the efficacy of the rTMS. For the purpose of this study, the term dose will be used to mean the number of rTMS sessions. Similarly, the term toxicity will correspond to efficacy of the rTMS.

First, we used the data by Wang et al. (2014) to determine the threshold value for a clinically meaningful change in connectivity. The optimal cut-point for dichotomizing FC change was 0.028, which was determined by maximizing the Youden’s index (sensitivity+specificity1) in the ROC analysis.

The details and assumptions to implement CRM are as follows.

- **Dose limiting toxicity (DLT):** We assume that a FC change equal to or greater than the threshold value 0.028 is an effective change. DLT will be defined as the FC change from baseline to post-stimulation ≥ 0.028
- **Target toxicity level (TTL):** The sensitivity for the dichotomized FC change (at 0.028) in the parietal stimulation group was 87.50% in Wang et al. (2014). TTL is set to 12.5%, which is equal to (1-sensitivity). *The MTD is then defined as the number of rTMS sessions that has a risk of DLT equal to the chosen TTL value of 12.5%.*
- **Dose levels:** The dose level refers to the number of consecutive rTMS sessions.

The range of sessions is 1 to 5.

- **Number of healthy volunteers per dose level:** 3 healthy volunteers per dose level
- **Dose-toxicity model:** We propose to use a one-parameter hyperbolic-tangent dose-response model by O'Quigley et al. (1990), where a Gamma (1, 1) prior will be used.
- **Starting dose:** 3 sessions
- **Stopping rule:** Healthy volunteers will continue to be recruited to the trial until a fixed sample size of 15 is achieved.

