The following aims will be investigated using the optimal sessions determined in Specific Aim 1.

ii. Experiment 2

Specific Aim 2 (Primary Aim 1): To determine whether rTMS delivered to the parietal cortex increases parietal-hippocampal FC in healthy subjects.

For each healthy subject, the Pearson correlation coefficients (r) between time courses of BOLD activity in the parietal and hippocampal areas will be calculated to determine the functional connectivity before and after rTMS stimulation. They will be Fisher-transformed to normalize r values. *We will call this the z scores.* The change in the z scores from pre- to post- stimulation will be assessed using the one-tailed, paired *t* test.

Specific Aim 3: To measure the effects of parietal rTMS on AMT and WPT-I.

First, the change in the AMT scores from pre- to post- stimulation will be calculated. Then, the two sample *t*-tests will be used to compare the changes in the AMT scores between the parietal and the sham groups. Additionally, we will consider using the Wilcoxon rank sum tests when the changes in the AMT scores are not normally distributed in each group.

Next, we will perform a similar analysis for WPT-I scores.

Specific Aim 4: To evaluate the relationship between fMRI connectivity and AMT and WPT-I outcomes in the parietal group in healthy subjects.

For each subject, the Pearson correlation coefficients (r) between time courses of the parietal and hippocampal regions will be calculated to determine the functional connectivity before and after rTMS stimulation. Then, the changes of the z scores (Fisher transformed r values) from pre- to post- simulation will be calculated. Similarly, the changes in AMT scores from pre- to post-simulation will be computed. The linear

regression models will be used to examine the relationship between the change in functional connectivity and the change in AMT scores.

Next, we will repeat a similar analysis using WPT-I scores.

b. Power analysis

Experiment 1: The maximum number of healthy subjects for Experiment 1 is set at 15.

Experiment 2: We propose to recruit 32 healthy participants (16 subjects in each of the parietal and control groups) to participate in Experiment 2.

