We based our sample size estimate on the behavioral results from the study we are replicating (Wang et al., 2014). In Wang et al. (2014), the effect size of the memory increases caused by PPC stimulation, compared to sham stimulation, was 0.75 (Cohen's d). This was achieved using a within-subjects design. Using this effect size, to achieve a β of 0.70 using the between subjects design described in this protocol (Experiment 2), 16 participants are required.

Sixteen subjects per group also achieves sufficient power to detect FC changes. Wang et al. indicate that the mean difference in FC from post to pre stimulation in retrosplenial region was 0.1018 and its standard deviation was 0.09296. Based on their data, we assume that the mean change will be between 0.1008 and 0.1028. We also assumed its standard deviation (SD) will be between 0.085 and 0.10. A one-tailed, paired t-test was used at a significance level of 0.05. Computations were carried out using PASS (Hinze J. [2008] PASS, NCSS, LLC, Kaysville, Utah).

The following table shows estimates of power to address Primary Aim 1 given ten subjects per treatment group.

Mean of paired difference	Estimated standard deviation of the difference	Power
0.1008	0.085	0.96440
0.1018	0.085	0.96698
0.1028	0.085	0.96940
0.1008	0.093	0.93446
0.1018	0.093	0.93833

0.1028	0.093	0.94202
0.1008	0.100	0.90159
0.1018	0.100	0.90651
0.1028	0.100	0.91125

Table 1. Estimated power for primary aim 1 (N=10 in parietal group)

A sample size of ten subjects per group achieves 93.8% power to detect a mean of paired differences of 0.1018 with an estimated standard deviation of differences of 0.093 and with a significance level of 5% using a one-sided paired t-test. Under other scenarios, the estimated powers were greater than 90%.

Assuming a 50% dropout rate, we anticipate enrolling up to 101 healthy subjects (33 for Experiment 1; 64 for Experiment 2).

11. Human Subjects Protection

a. Subject selection

We will recruit healthy participants through referrals from the NIH Clinical Research Volunteer program or through self-referrals to the protocol. We will work to ensure equitable selection.

b. Justification for exclusion of subjects

i. Justification for exclusion of children

Children will not be included. The study is predicated on the work of Wang et al. (2014) who studied participants over the age of 18. Therefore, in order to replicate this result, we will recruit a sample of the same age.

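### The 0.70 power for the AMT comparison at 16 per group is not established: a d of 0.75 from a within-subjects study is used unconverted for a two-sample test, and its scaling is not stated

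*Combined protocol and SAP*

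**What the plan says.** Section 10.b (Power analysis, Experiment 2) bases the sample size on the behavioural result of the study being replicated: "the effect size of the memory increases caused by PPC stimulation, compared to sham stimulation, was 0.75 (Cohen's d"). It then goes straight from one design to the other: "This was achieved using a within-subjects design. Using this effect size, to achieve a β of 0.70 using the between subjects design". That sentence ends by putting the requirement at 16 participants. The opening of the Experiment 2 paragraph makes clear that this means "16 subjects in each of the parietal and control groups", or 32 in all.

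The analysis being powered is in section 10.a.ii, Specific Aim 3: two-sample t-tests "will be used to compare the changes in the AMT scores between the parietal and the sham groups". The sham group there must be the vertex group, the only control in Experiment 2. Section 4.d.viii confirms that each participant receives stimulation at one site only. AMT change is a primary outcome (section 9.a) and the subject of a primary hypothesis (section 2.b).

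The documents give no SD basis for the 0.75, no SD of AMT change, no correlation between conditions and no conversion. Alpha and sidedness are given only for the functional connectivity (FC) calculation (one-tailed, 0.05), not for the AMT test.

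**The concern.** A standardised effect depends on the SD in its denominator. In a within-subjects study, d is commonly the mean stimulation-minus-sham difference divided by the SD of each person's difference. The planned two-sample test is instead governed by the SD, between people, of a single pre-to-post change. The two agree only in a special case. The plan notes the change of design and carries the number across without comment.

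This sentence is the only support for power on the AMT outcome. The FC calculation in the same section cannot stand in for it: it is a one-group paired test, tabulated for ten subjects, and does not address the parietal-versus-vertex contrast in memory. If the AMT comparison turns out null, how much that null says depends on the power, and at present the plan's figure for it cannot be relied on.

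**Working it through.** **Inputs.** From 10.b: d = 0.75, 16 per group, target 0.70. The target is written as β; read literally as a type II error it would mean 30% power, so it is taken as power. From 10.a.ii: two-sample t-test on change scores. Assumed, because not stated for the AMT: alpha 0.05, shown one-sided and two-sided.

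**Step 1: reproduce the plan's figure.** With 0.75 entered directly as a two-group d, the noncentrality is d × sqrt(n/2) = 0.75 × sqrt(16/2) = 2.121.

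- One-sided 0.05, normal approximation: Φ(2.121 − 1.645) = 0.683. Exact noncentral t, 30 df: 0.666.
- Two-sided 0.05, normal approximation: Φ(2.121 − 1.960) = 0.564. Exact t: 0.537.
- Per-group n for 0.70 by exact t: 17.4, so 18, one-sided; 22.9, so 23, two-sided.
- Other readings fit worse. A paired test with 16 people gives 0.89 one-sided or 0.80 two-sided. Sixteen in total (8 per group) gives 0.41 or 0.29.

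The stated figure is therefore approximately a one-sided 0.05 two-sample calculation with 0.75 unchanged. It comes close to 0.70 but does not reach it.

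**Step 2: 0.75 already on the between-person SD of change.** No conversion is needed and no correlation enters. The exact-t results of Step 1 apply: 0.67 one-sided, 0.54 two-sided.

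**Step 3: 0.75 a paired d (assumption).** Let σ be the between-person SD of one condition's memory change, assumed equal in both conditions, ρ the correlation of one person's changes across the two conditions, and Δ the mean difference. The SD of the paired difference is σ × sqrt(2(1 − ρ)), so

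- d_paired = Δ / [σ × sqrt(2(1 − ρ))]
- d_between = Δ / σ = 0.75 × sqrt(2(1 − ρ))

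The documents do not give ρ; the range 0 to 0.8 is assumed. Exact-t results at alpha 0.05:

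| ρ | d_between | Power, 16 per group, one-sided | Two-sided | n per group for 0.70, one-sided / two-sided |
|---|---|---|---|---|
| 0 | 1.06 | 0.90 | 0.83 | 10 / 13 |
| 0.25 | 0.92 | 0.81 | 0.71 | 12 / 16 |
| 0.5 | 0.75 | 0.67 | 0.54 | 18 / 23 |
| 0.7 | 0.58 | 0.48 | 0.36 | 29 / 38 |
| 0.8 | 0.47 | 0.37 | 0.26 | 43 / 56 |

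Power of 0.70 at 16 per group needs d = 0.785 one-sided or 0.908 two-sided. Solving ρ = 1 − (d/0.75)²/2 gives ρ = 0.45 or 0.27. Below that value the plan understates its power; above it, the plan overstates it.

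A third basis, the SD of raw memory scores, would need a different conversion through the pre-to-post correlation. That is not given either, and it is not computed here.

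**The case against.** The strongest reply is that the planners did use a two-sample calculation. They named both designs in adjacent sentences, and Step 1 shows that they did not borrow the precision of a paired test. Nothing in the documents says that 0.75 is a paired d. If it is already on the between-person SD of change, it needs no conversion. All of this stands, and it limits what can be said.

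A reader might infer that 0.70 does not belong to a 16-per-group design at all, or that it holds only at one value of ρ. The documents do not support either reading: both treat the paired scaling as settled, and under Step 2 ρ plays no part. A reader might also infer that the trial is underpowered by the transfer. That does not follow, because with a paired d and ρ below 0.5 the converted effect exceeds 0.75. It can further be argued that a ρ of 0.7 to 0.8 between two change scores is less plausible, since each carries error from two tests. That is a judgement; the documents give no figure to settle it.

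Finally, access to the source study's memory data cannot be presumed. Section 10.a.i shows its data being used only "to determine the threshold value for a clinically meaningful change in connectivity".

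What does not stand is the claim that the plan's figure is then sound. Even on the reading most favourable to the unconverted d, exact-t power is 0.67 one-sided. With a two-sided test, which the plan does not rule out for the AMT, it is 0.54.

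**Conclusion.** The power statement for a primary outcome is unsupported as written and should be replaced. This is an undocumented planning assumption, not a demonstrated shortfall. At face value d = 0.75 gives 0.67 one-sided or 0.54 two-sided, not 0.70. If 0.75 is a paired d, the power lies between 0.90 and 0.37 one-sided, or 0.83 and 0.26 two-sided, depending on a correlation that the plan does not mention.

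That 0.75 moves unconverted from a within-subjects result to a between-groups test is plain from the text. The size and direction of any error are not. They rest on the assumed alpha of 0.05, the assumed range of ρ, equal SDs in the two conditions, and a scaling that only the source study can settle.

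**What to change.** Rewrite the AMT sentence in 10.b to:

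- say how the 0.75 was scaled (paired difference, single-condition change or raw score);
- state the alpha and sidedness of the AMT two-sample t-test;
- call the target power rather than β, and give the sample size as 16 per group;
- replace the single 0.70 with the power of 16 per group for that test. If the source study can supply the mean stimulation-minus-sham difference in memory change and the between-person SD of a single-condition change, compute d_between from those. If not, give power over ρ from 0 to 0.8, as in the table above, with the face-value result (0.67 or 0.54) beside it.

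Keep n = 32. The cost is one paragraph and a small table, with no extra participants and no change to the analysis. The downside is that the stated power becomes a range and may be less favourable than 0.70.

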2. Study Objectives and hypotheses

The overall objective of this study is to determine whether functional connectivity can be used as a biomarker of rTMS synaptic modulation. The experiments outlined in this protocol will not be used to demonstrate the clinical effects of rTMS.

a. Aims

Experiment 1

Specific Aim 1: To determine the number of rTMS sessions required to produce a substantial change in FC between the parietal cortex and hippocampus in healthy subjects.

Experiment 2

Specific Aim 2: To determine whether rTMS delivered to the parietal cortex increases parietal-hippocampal FC in healthy subjects.

Specific Aim 3: To measure the effect of parietal rTMS on AMT and WPT-I, performance.

Specific Aim 4: To evaluate the relationship between fMRI connectivity and AMT and WPT-I outcomes after parietal rTMS in healthy subjects.

b. Hypotheses

i. Primary Hypotheses

Experiment 2: rTMS of the left parietal cortex will increase FC between the left parietal cortex and the hippocampus compared to rTMS of the vertex. rTMS of the left parietal cortex will significantly increase explicit memory compared to rTMS of the vertex.

ii. Secondary hypotheses:

Experiment 2: rTMS of the left parietal cortex will decrease FC between the left caudate (head) and parietal cortex compared to rTMS of the vertex. rTMS of the left parietal cortex will significantly decrease implicit memory compared to rTMS of the vertex.

3. Subjects

a. Description of study populations

We will study 50 healthy individuals (Experiment 1: 18; Experiment 2: 32). We are requesting up to 101 healthy volunteers as the accrual ceiling to account for dropouts and screening failures.

b. Inclusion criteria

Healthy individuals in Experiments 1 and 2.

- Age 18-50 (inclusive)
- English speaking and writing

c. Exclusion criteria

- Any current major neurological or psychiatric disorder such as (but not limited to) stroke, Parkinson disease, Alzheimer disease, schizophrenia or major depression
- History of seizure
- Medications acting on the central nervous system
- Ferromagnetic metal in the cranial cavity or eye, implanted neural stimulator, cochlear implant, or ocular foreign body
- Implanted cardiac pacemaker or auto-defibrillator or pump
- Non-removable body piercing
- Claustrophobia
- Inability to lie supine for 1 hour
- Pregnancy, nursing, or plans to become pregnant during the study.
- Members of the NINDS Behavioral Neurology Unit (BNU)
- For Experiment 2: Participation in Experiment 1

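### The primary AMT comparison has no stated alpha or sidedness; at alpha 0.05, 16 per group gives 66.6% power one-sided or 53.7% two-sided, against the 70% claimed

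*Combined protocol and SAP*

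**What the plan says.** Section 9.a lists the pre-to-post change in AMT score as one of two primary outcomes; the other is the change in parieto-hippocampal functional connectivity (FC). The AMT hypothesis in section 2.b.i is directional: "rTMS of the left parietal cortex will significantly increase explicit memory compared to rTMS of the vertex".

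AMT drives the sample size. Section 10.b says "We based our sample size estimate on the behavioral results from the study we are replicating", takes Cohen's d = 0.75 from that study's within-subjects comparison, and concludes that "to achieve a β of 0.70 using the between subjects design described in this protocol (Experiment 2), 16 participants are required". Section 10.b also gives the allocation: "16 subjects in each of the parietal and control groups".

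Under Specific Aim 3 (section 10.a.ii), two-sample t-tests "will be used to compare the changes in the AMT scores between the parietal and the sham groups", with Wilcoxon rank sum tests as the fallback if the changes are not normally distributed.

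Sidedness and alpha are given only for FC. Specific Aim 2 says the FC change "will be assessed using the one-tailed, paired" t test, and the FC power paragraph says "A one-tailed, paired t-test was used at a significance level of 0.05".

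**The concern.** A sample size for a t-test depends on effect size, power, alpha and number of tails. For AMT the plan gives the first two. The last two are missing from both the power paragraph and the analysis section, although the plan states both for FC.

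Two things are at stake. First, a reader cannot tell whether 16 per group delivers the claimed power: one-sided the figure is nearly right, two-sided it is well short. Second, the decision rule for a primary outcome stays open. With 32 participants, the gap between the one-sided and two-sided critical values covers a realistic range of results, so the same data could be called positive or negative by a choice made after they are seen.

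**Working it through.** **Inputs**

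- Effect size d = 0.75 (section 10.b).
- n = 16 per group, so df = 2 × 16 − 2 = 30 (section 10.b).
- Target power 70%. Section 10.b writes this as β = 0.70. Read literally that is 30% power; with a two-sample t-test at alpha 0.05 this needs only 6 per group one-sided or 9 two-sided. With 16 in each group, 70% power is the sensible reading.
- Alpha: not stated for AMT. Assumed 0.05, the level used for FC.
- Sidedness: not stated for AMT. Both are computed.

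**Check of the method on the plan's own figures.** Table 1 (FC, n = 10, paired, one-sided 0.05) is a benchmark. For mean 0.1018 and SD 0.093, the noncentrality is (0.1018 / 0.093) × √10 = 3.4615 and the critical t on 9 df is 1.8331. The noncentral t gives power 0.93833, exactly as printed; this is the value reported in "A sample size of ten subjects per group achieves 93.8% power to detect a mean of paired differences of 0.1018". All nine entries of Table 1 reproduce to five decimals in this way. The normal approximation (0.96536) and a two-sided exact t (0.86767) do not match.

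**AMT power at 16 per group.** Noncentrality = d × √(n/2) = 0.75 × √8 = 2.121. Power is the probability that a noncentral t on 30 df exceeds the critical value; for the two-sided test the negligible lower tail is added.

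| alpha 0.05 | Critical t | Exact power, n = 16 | Normal approximation, n = 16 | n per group for 70%, exact |
|---|---|---|---|---|
| One-sided | 1.697 | 66.6% | 68.3% | 18 (17 gives 69.0%, 18 gives 71.2%) |
| Two-sided | 2.042 | 53.7% | 56.4% | 23 (22 gives 68.1%, 23 gives 70.1%) |

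The shortfall against 70% is 70 − 66.6 = 3.4 points one-sided and 70 − 53.7 = 16.3 points two-sided.

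The normal approximation for the sample size, n = 2(z₁₋α + z₀.₇₀)² / d², gives:

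- one-sided: 2 × (1.645 + 0.524)² / 0.5625 = 16.7, so 17;
- two-sided: 2 × (1.960 + 0.524)² / 0.5625 = 21.9, so 22.

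The stated 16 is therefore approximately recovered under one-sided 0.05 and not under two-sided 0.05.

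**Detectable effect.** With 16 per group, 70% power corresponds to d = 0.78 one-sided and d = 0.91 two-sided.

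**Effect of the open choice on the result.** The smallest observed d that reaches significance is the critical t × √(2/16):

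- one-sided: 1.697 × 0.3536 = 0.600;
- two-sided: 2.042 × 0.3536 = 0.722.

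If the true d is 0.75, the probability of an observed d between these values is 0.6658 − 0.5372 = 0.129 (the omitted lower tail is negligible), or about 13%.

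**The case against.** The strongest reply is that the plan means a one-sided test at 0.05. The AMT hypothesis is directional, the only sidedness stated anywhere is one-tailed, the only alpha is 0.05, and this is the reading that comes close to 16 per group. The gap is then 1 or 2 people per group, or 1.7 to 3.4 points of power depending on the formula, which is the size of a method or rounding difference. Much of this stands. One-sided is the more plausible reading, and on it the shortfall is small. But a directional hypothesis does not specify a one-sided test. The plan wrote one-tailed for FC in both the analysis and the power text, and in neither for AMT.

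The exact-t benchmark can also be questioned. Table 1 shows how FC power was computed, but the documents do not say how the AMT figure of 16 was obtained. That is fair, so a 3.4-point gap should not be presented as a proven slip. The normal approximation still gives less than 70%.

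A third reply is that the effect size is the larger uncertainty. The 0.75 comes from a within-subjects study, and the documents do not say how it was standardised. If it was divided by the SD of within-person differences, the between-group value is 0.75 × √(2(1 − r)), where r is the within-person correlation. Assuming r from 0.3 to 0.7, d runs from 0.89 to 0.58, and power at 16 per group runs from 79% to 48% one-sided or 68% to 36% two-sided. This is correct. It is a reason to state the assumption as well, not a reason to leave the test undefined.

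**Conclusion.** The concern holds. Alpha and sidedness are missing for the test of a primary outcome that sets the sample size, and the claimed 70% power is not reached on either reading at alpha 0.05. One-sided, power is 66.6%, a minor shortfall. Two-sided, it is 53.7%, a material shortfall, but on that reading only.

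These figures rest on an assumed alpha of 0.05, on reading β as power, on d = 0.75 holding between groups, and on all 16 per group being analysed. They assume no adjustment for having two primary outcomes. If alpha were split to 0.025, power would be 53.7% one-sided or 41.7% two-sided.

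This should be fixed. The stronger reason is the undefined decision rule; the missing points of power on the one-sided reading matter less.

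**What to change.** Before AMT data are analysed by group, choose the test and replace the power sentence in section 10.b with one of the following.

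- One-sided: *The change in AMT score will be compared between groups with a two-sample t-test at one-sided alpha 0.05. With 16 per group and d = 0.75, power is 67%; the effect detectable with 70% power is d = 0.78.*
- Two-sided: *The change in AMT score will be compared between groups with a two-sample t-test at two-sided alpha 0.05. With 16 per group and d = 0.75, power is 54%; the effect detectable with 70% power is d = 0.91.*

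In either case, write power in place of β and add: *The d of 0.75 comes from a within-subjects study and is assumed to apply between groups.*

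Repeat the chosen alpha and sidedness under Specific Aim 3 and apply them to the Wilcoxon fallback too. State whether alpha is adjusted for the two primary outcomes; if it is, recompute the power.

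The change is wording only and adds no participants. The cost is a less favourable stated power: slightly so one-sided, clearly so two-sided.

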To reduce the risks of hearing loss associated with rTMS, all subjects will be fitted with hearing protection.

8. Subject Safety Monitoring

For healthy subjects, a credentialed physician or nurse practitioner will be on site for all rTMS administration and immediately available. This is the standard of care in community and academic clinical and experimental rTMS centers, nationwide. Study staff will be trained in rTMS administration, rTMS safety, and the measurement of the motor evoked potential threshold and will have performed 10 measurements under supervision. Study staff will monitor individuals during participation and participants will be encouraged to tell experimenters of any discomfort. Any subject exhibiting distress or who wishes to stop the experiment for any reason will be allowed to stop. Participants may withdraw at any time. Data of those participants that have completed at least the first session of either Experiment 1-2 (i.e. both MRI scan and behavioral assessment) will be kept and analyzed. A researcher may end experimentation for the following reasons:

- 1) Abnormal response to rTMS including the occurrence of a seizure, loss of consciousness, or excessive pain or headache produced by rTMS.
- 2) Withdrawal of consent and/or decision to terminate.
- 3) Excessive frustration exhibited by participants on behavioral tasks.
- 4) Decision by legal proxy or patient guardian to terminate participation.
- 5) Subjects withdrawn due to high motor thresholds above the maximum capacity of the stimulator
- 6) Subjects withdrawn due to discomfort of TMS

9. Outcome Measures

a. Primary outcome measures

- Pre-to-post rTMS difference in FC between the left parietal cortex and the left hippocampus (Experiments 1-2) in healthy subjects (Experiments 1 and 2).
- Pre-to-post rTMS difference in AMT scores in healthy subjects (Experiment 2).

b. Secondary outcome measures

- Pre-to-post rTMS difference in WPT-I scores after rTMS in healthy subjects (Experiment 2).

c. Exploratory outcome measures

- Correlations between memory performance and white matter integrity (Experiment 2).

10. Statistical Analysis

a. Analysis of data/study outcomes

i. Experiment 1

Specific Aim 1: To determine the number of rTMS sessions required to produce a substantial change in FC between the parietal cortex and hippocampus in healthy subjects.

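### The power shown for Primary Aim 1 comes from retrosplenial inputs, ten subjects and a parietal-only paired test; none is shown for parietal-hippocampal FC change relative to vertex

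*Combined protocol and SAP*

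**What the plan says.** - **Outcome (9.a):** "Pre-to-post rTMS difference in FC between the left parietal cortex and the left hippocampus".
- **Hypothesis (2.b.i, Experiment 2):** "rTMS of the left parietal cortex will increase FC between the left parietal cortex and the hippocampus compared to rTMS of the vertex".
- **Test for Primary Aim 1 (10.a.ii, Specific Aim 2):** "The change in the z scores from pre- to post- stimulation will be assessed using the one-tailed, paired" *t* test. No vertex term appears.
- **Test for AMT (10.a.ii, Specific Aim 3):** two-sample tests are used to "compare the changes in the AMT scores between the parietal and the sham groups". The vertex arm is called sham here.
- **Planned size (10.b):** "16 subjects in each of the parietal and control groups", which the text says is also enough for the FC changes.
- **Basis for that statement (10.b):** "the mean difference in FC from post to pre stimulation in retrosplenial region was 0.1018 and its standard deviation was 0.09296". The mean is then varied from 0.1008 to 0.1028 and the SD from 0.085 to 0.10. Table 1 gives "estimates of power to address Primary Aim 1 given ten subjects per treatment group". The text reports 93.8% for the central case and adds "Under other scenarios, the estimated powers were greater than 90" per cent.

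**The concern.** Table 1 is presented as power for Primary Aim 1, but it differs from the primary FC question in three ways.

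1. **Pathway.** The mean and SD are retrosplenial. The documents give no mean or SD of change for the parietal-hippocampal pair, and no reason why the retrosplenial values should stand in for it.
2. **Comparison.** The hypothesis is relative to vertex, whereas the table concerns change within the parietal group alone.
3. **Sample size.** The table uses 10; the plan is 16 per group.

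The second is the root problem, because the planned Aim 2 test has the same gap. Section 1.d includes the vertex arm to control for sensory and other nonspecific effects of rTMS. A paired test in the parietal group cannot separate a site-specific effect from a nonspecific one or from change on repeat scanning. It could be significant without supporting the hypothesis in 2.b.i, and a reassuring power table built on the same test hides this.

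**Working it through.** **Inputs.** From 10.b: mean change 0.1008, 0.1018 or 0.1028; SD 0.085, 0.093 or 0.100; one-sided alpha 0.05; N=10 in Table 1 and n=16 per group planned. Not in the documents, so assumed for the vertex comparison: mean vertex change 0, the same SD in both groups, and the retrosplenial values carried over to the primary pathway.

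**Formulas (exact noncentral *t*).**
- Paired: df = n − 1, noncentrality = (mean/SD) × √n.
- Two-sample: df = 2n − 2, noncentrality = (difference/SD) × √(n/2).
- Power is the probability that the noncentral *t* exceeds the critical value.

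**Step 1: reproduce Table 1.** At 0.1018/0.093 with n=10, noncentrality = 1.0946 × 3.1623 = 3.46, df 9, critical value 1.833, power 0.93833. All nine cells agree to five decimals. The table is a correct calculation of a one-sided, within-group test.

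**Step 2: same test at the planned n=16.** Noncentrality = 1.0946 × 4 = 4.38, df 15, power 0.9942. Over the nine scenarios the range is 0.9860 to 0.9985. The ten-subject figure therefore understates power for the test as planned.

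**Step 3: parietal versus vertex, 16 per group.** At 0.1018/0.093, noncentrality = 1.0946 × √8 = 3.10, df 30. The one-sided critical value is 1.697, giving power 0.916. The two-sided value is 2.042, giving 0.850.

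| Mean / SD | Table 1 (paired, n=10) | Paired, n=16 | Two-sample 16/16, one-sided | Two-sample 16/16, two-sided |
|---|---|---|---|---|
| 0.1008 / 0.085 | 0.964 | 0.998 | 0.949 | 0.901 |
| 0.1018 / 0.085 | 0.967 | 0.998 | 0.952 | 0.906 |
| 0.1028 / 0.085 | 0.969 | 0.998 | 0.955 | 0.911 |
| 0.1008 / 0.093 | 0.934 | 0.994 | 0.912 | 0.843 |
| 0.1018 / 0.093 | 0.938 | 0.994 | 0.916 | 0.850 |
| 0.1028 / 0.093 | 0.942 | 0.995 | 0.921 | 0.857 |
| 0.1008 / 0.100 | 0.902 | 0.986 | 0.873 | 0.788 |
| 0.1018 / 0.100 | 0.907 | 0.987 | 0.879 | 0.796 |
| 0.1028 / 0.100 | 0.911 | 0.988 | 0.884 | 0.803 |

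One-sided, three of nine scenarios fall below 90%; two-sided, six of nine.

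**Step 4: sensitivity to the borrowed effect.** The means in Table 1 span only about ±1% (0.001/0.1018). Its standardised effects run from 0.1008/0.100 = 1.01 to 0.1028/0.085 = 1.21. With SD 0.093 and the pathway effect set, as an assumption, to a fraction of 0.1018:

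| Effect | Paired, n=16 | Two-sample, one-sided | Two-sample, two-sided |
|---|---|---|---|
| 125% (0.1273) | >0.99 | 0.98 | 0.96 |
| 100% (0.1018) | 0.99 | 0.92 | 0.85 |
| 75% (0.0764) | 0.93 | 0.73 | 0.61 |
| 50% (0.0509) | 0.67 | 0.45 | 0.32 |

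**Step 5: break-even at SD 0.093.** One-sided between-group power reaches 90% only if the difference is at least 0.0985 (97% of 0.1018), and 80% only if it is at least 0.0837 (82%). For the paired test at n=16 the limits are 0.0714 (70%) and 0.0606 (60%).

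**Step 6: vertex change (assumption).** If vertex FC rises by 0.01 or 0.02, the difference becomes 0.0918 or 0.0818 and one-sided power falls from 91.6% to 86% or 78%. A fall in vertex FC would raise it.

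**The case against.** The best defence is that Table 1 matches most of the plan. Specific Aim 2 names no comparator, the outcome in 9.a is a pre-to-post difference, and the test in 10.a.ii is the one used in the table. The arithmetic is right, and the N=10 error is conservative. The sample size itself rests on the memory outcome. The greater-than-90% figure is reported as a result, not set as a target, and every one-sided vertex scenario on the plan's inputs exceeds 80%. Section 4.d.iii says the replicated study found no significant effect of off-target stimulation on connectivity, which lends some support to assuming no vertex change. The FC plan is one-tailed, so the two-sided figures describe a test it does not propose.

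Much of this stands. The two-sided figures are context only. The 50-125% range is illustrative, since the documents support no particular range. A non-significant off-target effect makes zero change plausible but does not establish it. What the defence does not answer is that 2.b.i states the primary FC hypothesis against vertex while neither test nor table includes vertex. That the table agrees with the test means both need correcting. Nor does disclosing the region of origin justify using its values for another pathway.

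**Conclusion.** The concern holds. Table 1 is correct for what it calculates, but it does not show power for parietal-hippocampal FC change relative to vertex. For that comparison at 16 per group, the plan's own inputs give 87.3-95.5% one-sided (91.6% at 0.1018/0.093), against 98.6-99.8% for the planned paired test. These between-group figures rest on three assumptions: retrosplenial values apply to the primary pathway, vertex change is zero, and SDs are equal.

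This does not show that the trial is underpowered for FC; the pathway effect could be larger or smaller than the retrosplenial one. It shows that adequacy is asserted without support and that the margin is thin: a 25% smaller effect at SD 0.093 takes one-sided between-group power to 73%. The more serious consequence is inferential, since following 10.a.ii as written could declare the primary FC hypothesis met without using the control arm.

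**What to change.** 1. **10.a.ii, Specific Aim 2.** Make the primary test a two-sample comparison, parietal versus vertex, of the pre-to-post change in Fisher-z parietal-hippocampal FC, with sidedness stated, as Aim 3 already does for AMT. Keep the paired test within the parietal group as supportive.
2. **10.b, Table 1.** Replace it with power for that comparison at 16 per group. Use the parietal-hippocampal mean and SD from the source data if available; otherwise label the retrosplenial values as a proxy. Cover a wider range of effects, for example 50-125% of the assumed value, and state the assumed vertex change.
3. **10.b, text.** Delete the ten-subject wording and restate the power. For example: 16 per group gives 87-96% power (one-sided 5% two-sample *t* test) for a difference of 0.1008-0.1028 with SD 0.085-0.10, using retrosplenial values as a proxy and assuming no vertex change; power is 73% and 45% at 75% and 50% of 0.1018 with SD 0.093.

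The cost is one changed analysis sentence, one recalculation and a replacement table, with no added participants. The stated power becomes less favourable: 91.6% instead of 99.4% at 0.1018/0.093 and n=16. Because this changes the test for a primary outcome, it should be made before FC results are examined by group; the documents mark Experiment 1 as completed but do not give the status of Experiment 2.
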